5.5.3 Rescue Medications & Supportive Care

Participants should receive appropriate supportive care measures as deemed necessary by the treating investigator. Suggested supportive care measures for the management of AEs with potential immunologic etiology are outlined along with the dose modification guidelines in

A Phase II, Single-arm Study of Combination Pembrolizumab and Olaparib in the Treatment of

Patients with Advanced Cholangiocarcinoma

Version 2.1: 17Mar2023

Section 5.2.2, [Table 3]. Where appropriate, these guidelines include the use of oral or IV treatment with corticosteroids, as well as additional anti-inflammatory agents if symptoms do not improve with administration of corticosteroids. Note that several courses of steroid tapering may be necessary as symptoms may worsen when the steroid dose is decreased. For each disorder, attempts should be made to rule out other causes such as metastatic disease or bacterial or viral infection, which might require additional supportive care. The treatment guidelines are intended to be applied when the Investigator determines the events to be related to pembrolizumab.

Note: If after the evaluation of the event, it is determined not to be related to pembrolizumab, the Investigator does not need to follow the treatment guidance. Refer to [Table 3] in Section 5.2.2 for guidelines regarding dose modification and supportive care.

It may be necessary to perform conditional procedures such as bronchoscopy, endoscopy, or skin photography as part of evaluation of the event.

5.6 Participant Withdrawal/Discontinuation Criteria

Participants may discontinue study treatment at any time for any reason or be dropped from the study treatment at the discretion of the investigator should any untoward effect occur. In addition, a participant may be discontinued from study treatment by the investigator or the Sponsor if study treatment is inappropriate, the trial plan is violated, or for administrative and/or other safety reasons. Specific details regarding procedures to be performed at study treatment discontinuation are provided in Section 7.1.4 – Other Procedures.

A participant must be discontinued from study treatment but continue to be monitored in the study for any of the following reasons:

- The participant or participant's legally acceptable representative requests to discontinue study treatment
- Confirmed radiographic disease progression outlined in Section 7.1.2.6
- Any progression or recurrence of any malignancy, or any occurrence of another malignancy that requires active treatment
- Unacceptable adverse experiences as described in Section 5.2.2.
- The participant has a medical condition or personal circumstance that, in the opinion of the investigator and/or sponsor, placed the participant at unnecessary risk from continued administration of study treatment.
- The participant has a confirmed positive serum pregnancy test
- Noncompliance with study treatment or procedure requirements

A Phase II, Single-arm Study of Combination Pembrolizumab and Olaparib in the Treatment of

Patients with Advanced Cholangiocarcinoma

Version 2.1: 17Mar2023

- Recurrent Grade 2 pneumonitis
- Discontinuation of treatment may be considered for participants who have attained a confirmed complete response (CR) and have been treated for at least 8 cycles (at least 24 weeks), receiving 2 doses of pembrolizumab and at least 80% of the planned doses of olaparib beyond the date when the initial CR was declared. These participants may be eligible for second course treatment described in Section 5.2.3.
- The participant is lost to follow-up
- Completion of 35 treatments (approximately 2 years) with pembrolizumab

Note: The number of treatments is calculated starting with the first dose. Participants who stop the combination or pembrolizumab after receiving 35 doses may be eligible for retreatment if they progress after stopping study treatment provided they meet the requirements detailed in Section 5.2.3. Participants may be retreated in the Second Course Phase (Retreatment) for up to an additional 17 cycles (approximately 1 year).

- Administrative reasons

5.7 Participant Replacement Strategy

Subjects who have not completed the 1st cycle of combination therapy can be replaced.

5.8 Clinical Criteria for Early Trial Termination

Early trial termination will be the result of the criteria specified below:

1. Quality or quantity of data record is inaccurate or incomplete
2. Poor adherence to protocol and regulatory requirements
3. Incidence or severity of adverse drug reaction in this or other studies indicates a potential health hazard to participants
4. Plans to modify or discontinue the development of the study drug

In the event of Merck decision to no longer supply study drug, ample notification will be provided so that appropriate adjustments to participant treatment can be made.

6.0 TRIAL FLOW CHART

6.1 Study Flow Chart

Study Evaluation	Screening	On Treatment Cycle 1-n	Follow Up Visit (1)	Follow Up Visit (2)	Long Term Follow Up ¹⁰	Survival Follow Up ¹¹
Cycle = 21 days	≤ 28 days	Day 1	30 days post last dose ± 7 days	6 weeks after Visit 1 ± 7 days	Every 12 weeks after Visit 2	Every 12 weeks after Visit 2
REQUIRED ASSESSMENTS						
Informed Consent	X					
Medical History ¹	X					
Diagnosis and Staging ²	X					
Physical Exam	X	X ⁹	X	X		
Vital signs and ECOG Performance Status ³	X	X ⁹	X	X		
AEs & concomitant medications	X	X ⁹	X	X		
LABORATORY ASSESSMENTS						
Complete Blood Cell Count with diff (CBC)	X	X ⁹	X	X		
Comprehensive Metabolic Profile (CMP) and amylase	X	X ⁹	X	X		

A Phase II, Single-arm Study of Combination Pembrolizumab and Olaparib in the Treatment of Patients with Advanced Cholangiocarcinoma
 Version 2.1: 17Ma2023

Study Evaluation	Screening	On Treatment Cycle 1-n	Follow Up Visit (1)	Follow Up Visit (2)	Long Term Follow Up ¹⁰	Survival Follow Up ¹¹
Cycle = 21 days	≤ 28 days	Day 1	30 days post last dose ± 7 days	6 weeks after Visit 1 ± 7 days	Every 12 weeks after Visit 2	Every 12 weeks after Visit 2
PT/INR and aPTT	X	X ⁹	X	X		
Thyroid Function (TSH, free T4, T3)	X	X ⁹	X	X		
Urinalysis	X	X ⁹	X	X		
Pregnancy test (serum or urine) (WOCBP) ⁴	X					
Carbohydrate antigen (CA) 19-9		X ¹⁰	X	X		
DISEASE ASSESSMENT						
CT of chest ⁵	X		X	X	X	
CT or MRI of abdomen and pelvis ⁵	X		X	X	X	
MRI Brain ⁵	X		X	X	X	
TREATMENT EXPOSURE						
Olaparib ⁶		X				
Pembrolizumab ⁶		X				
SPECIMEN COLLECTION						

A Phase II, Single-arm Study of Combination Pembrolizumab and Olaparib in the Treatment of Patients with Advanced Cholangiocarcinoma
 Version 2.1: 17Ma2023

Study Evaluation	Screening	On Treatment Cycle 1-n	Follow Up Visit (1)	Follow Up Visit (2)	Long Term Follow Up ¹⁰	Survival Follow Up ¹¹
Cycle = 21 days	≤ 28 days	Day 1	30 days post last dose ± 7 days	6 weeks after Visit 1 ± 7 days	Every 12 weeks after Visit 2	Every 12 weeks after Visit 2
Archival or Newly Obtained Tumor Tissue ⁷	X	X ⁸				
Blood Samples ⁸	X	X	X			
FOLLOW-UP						
Survival Status, Subsequent Therapy					X	X

KEY TO FOOTNOTES

¹ MEDICAL HISTORY SHOULD INCLUDE SMOKING AND ALCOHOL/CARBONATED BEVERAGE HISTORY AS WELL AS HOW THE SUBJECT LEARNED ABOUT THIS STUDY.

² DIAGNOSES AND STAGING TO INCLUDE: REVIEWING PATHOLOGY REPORT AND SCREENING SCANS.

³ VITAL SIGNS TO INCLUDE BLOOD PRESSURE, WEIGHT, AND HEIGHT (SCREENING ONLY) AND ECOG PERFORMANCE STATUS

⁴ FOR WOMEN OF CHILDBEARING POTENTIAL (WOCBP): URINE OR SERUM BHCG, WITHIN 28 DAYS OF REGISTRATION AND ONLY IF CLINICALLY APPROPRIATE. IF A URINE TEST IS DONE AND IT IS POSITIVE OR CANNOT BE CONFIRMED AS NEGATIVE, A SERUM PREGNANCY TEST WILL BE REQUIRED.

⁵ RADIOLOGY IMAGING FOR DISEASE ASSESSMENT WILL BE PERFORMED AT THE FOLLOWING TIME POINTS: SCREENING, EVERY SIX WEEKS WITHIN THE 24 WEEKS FROM THE START OF TREATMENT, THEN EVERY NINE WEEKS UP TO 12 MONTHS FROM THE START OF TREATMENT, THEN EVERY TWELVE WEEKS UP TO 24 MONTHS. FOR PATIENTS WHO DO NOT HAVE RADIOGRAPHIC PROGRESSION: RADIOLOGY IMAGING OR REPORT SHOULD BE OBTAINED EVERY 12 WEEKS THEREAFTER UNTIL DISEASE (RADIOGRAPHIC) PROGRESSION IF POSSIBLE. MRI OF THE BRAIN SHOULD ONLY BE DONE IF THE PATIENT IS SUSPECTED TO HAVE A BRAIN LESION.

A Phase II, Single-arm Study of Combination Pembrolizumab and Olaparib in the Treatment of Patients with Advanced Cholangiocarcinoma
Version 2.1: 17Ma2023

⁶ OLAPARIB WILL START ON C1D1 AND CONTINUE TWICE DAILY. PEMBROLIZUMAB WILL START C1D1 AND CONTINUE EVERY 3 WEEKS. PLEASE SEE SECTION 5 FOR DETAILS REGARDING OLAPARIB AND PEMBROLIZUMAB ADMINISTRATION.

⁷ ALL SUBJECTS WILL HAVE A BIOPSY PERFORMED OF A SAFELY ACCESSIBLE TUMOR BEFORE STARTING TREATMENT (WITHIN 42 DAYS OF STARTING TREATMENT ON THIS PROTOCOL) AND THE 3RD WEEK PRIOR TO 2ND DOSE OF PEMBROLIZUMAB, AND AT THE TIME OF CANCER PROGRESSION. SUBJECTS FOR WHOM NEWLY OBTAINED SAMPLES CANNOT BE PROVIDED (E.G. INACCESSIBLE OR SUBJECT SAFETY CONCERN) MAY SUBMIT AN ARCHIVED SPECIMEN ONLY UPON AGREEMENT FROM THE SPONSOR-INVESTIGATOR. SUBSEQUENT BIOPSIES CAN BE WAIVED BY SPONSOR-INVESTIGATOR FOR SAFETY CONCERNS OF THE BIOPSY PROCEDURE.

⁸ SERIAL BLOOD SAMPLES WILL BE COLLECTED TO SUPPORT BIOMARKER RESEARCH AT THE FOLLOWING TIME POINTS: PRIOR TO TREATMENT (1) C1D1, (2) C2D1, (3)C3D1 AND (5) FOLLOW UP VISIT 1. SEE CLM FOR ADDITIONAL DETAILS.

⁹ THIS TESTING IS TO BE DONE PRIOR TO EACH PEMBROLIZUMAB TREATMENT.

¹⁰ CARBOHYDRATE ANTIGEN (CA) 19-9 WILL BE DRAWN EVERY OTHER CYCLE STARTING AT CYCLE 1 (E.G. CYCLE 1, CYCLE 3, CYCLE 5, ETC).

¹¹ FOLLOW UP FOR PATIENTS THAT HAVE NOT EXPERIENCED PROGRESSION WILL OCCUR EVERY 12 WEEKS \pm 7 DAYS; THIS MAY BE DONE BY PHONE CALL OR OTHER AVENUES, AS APPROPRIATE. EVERY EFFORT SHOULD BE MADE TO OBTAIN INFORMATION ON RADIOLOGY SCANS OR OTHER TYPES OF DISEASE ASSESSMENT DOCUMENTATION.

¹² ONCE A SUBJECT EXPERIENCES CONFIRMED DISEASE PROGRESSION OR STARTS A NEW ANTI-CANCER THERAPY, THE SUBJECT MOVES INTO THE SURVIVAL FOLLOW-UP PHASE AND SHOULD BE CONTACTED BY TELEPHONE EVERY 12 WEEKS \pm 7 DAYS TO ASSESS FOR SURVIVAL STATUS UNTIL DEATH, WITHDRAWAL OF CONSENT, OR THE END OF THE STUDY, WHICHEVER OCCURS FIRST.

Hematology	Chemistry	Urinalysis	Other
Hematocrit	Albumin	Blood	Serum β -human chorionic gonadotropin [†]
Hemoglobin	Alkaline phosphatase	Glucose	(β -hCG) [†]
Platelet count	Alanine aminotransferase (ALT)	Protein	PT (INR)
WBC (total and differential)	Aspartate aminotransferase (AST)	Specific gravity	aPTT
Red Blood Cell Count	Total protein	Microscopic exam (If abnormal)	Total triiodothyronine (T3)

A Phase II, Single-arm Study of Combination Pembrolizumab and Olaparib in the Treatment of Patients with Advanced Cholangiocarcinoma
 Version 2.1: 17Ma2023

Hematology	Chemistry	Urinalysis	Other
Absolute Neutrophil Count	Carbon Dioxide ‡	results are noted	Free thyroxine (T4)
Absolute Lymphocyte Count	(CO ₂ or bicarbonate)	Urine pregnancy test †	Thyroid stimulating hormone (TSH)
	Sodium		Blood for correlative studies
	Calcium		
	Chloride		
	Glucose		
	Phosphorus		
	Potassium		
	Blood Urea Nitrogen		
	creatinine		
	Total Bilirubin		
	Direct Bilirubin (If total bilirubin is elevated above the upper limit of normal)		
	amylase		

† Perform on women of childbearing potential only. If urine pregnancy results cannot be confirmed as negative, a serum pregnancy test will be required.

‡ If considered standard of care in your region.

A Phase II, Single-arm Study of Combination Pembrolizumab and Olaparib in the Treatment of Patients with Advanced Cholangiocarcinoma

Version 2.1: 17Mar2023

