5.2 Inclusion Criteria

Subject must meet all of the following applicable inclusion criteria to participate in this study:

1. Be willing and able to provide written informed consent/assent for the trial.
2. Be ≥ 18 years of age on day of signing informed consent.

A Phase II, Single-arm Study of Combination Pembrolizumab and Olaparib in the Treatment of Patients with Advanced Cholangiocarcinoma

Version 2.1: 17Mar2023

3. Patients must have received 1 line of prior systemic therapy for metastatic or resectable disease (i.e. patients may have received adjuvant gemcitabine and then later platin-based therapy for recurrent metastatic disease)
4. Histological confirmation of cholangiocarcinoma manifesting as either intrahepatic, extrahepatic or gallbladder cancer. Patients with ampullary cancer are excluded.
5. Have measurable disease based on RECIST 1.1.
6. Be willing to provide tissue from a newly obtained core or excisional biopsy of a tumor lesion. Newly obtained is defined as a specimen obtained up to 6 weeks (42 days) prior to initiation of treatment on Day 1. Subjects for whom newly obtained samples cannot be provided (e.g. inaccessible or subject safety concern) may submit an archived specimen only upon agreement from the sponsor-investigator. Subjects from whom a biopsy is not medically possible or safe may be enrolled on the study upon agreement from the principal investigator.
7. Have a performance status of 0 or 1 on the ECOG Performance Scale.
8. Demonstrate adequate organ function as defined in Table 1. All screening labs will be performed within 28 days of registration.

Table 1: Adequate Organ Function Laboratory Values

System	Laboratory Value
Hematological	
Absolute neutrophil count (ANC)	$\geq 1,500 / \mu\text{L}$
Platelets	$\geq 100,000 / \mu\text{L}$
Hemoglobin	$\geq 9 \text{ g/dL}$ or $\geq 5.6 \text{ mmol/L}$ without transfusion or EPO dependency (within 7 days of assessment)
Renal	
Serum creatinine OR Measured or calculated ^a creatinine clearance (GFR can also be used in place of creatinine or CrCl)	$\leq 1.5 \times$ upper limit of normal (ULN) OR $\geq 50 \text{ mL/min}$ for subject with creatinine levels $> 1.5 \times$ institutional ULN
Hepatic	

A Phase II, Single-arm Study of Combination Pembrolizumab and Olaparib in the Treatment of Patients with Advanced Cholangiocarcinoma
 Version 2.1: 17Mar2023

Serum total bilirubin	$\leq 2.0 \times \text{ULN}$

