AST (SGOT) and ALT (SGPT)	$\leq 3.0 \times \text{ULN}$ OR $\leq 5 \times \text{ULN}$ for subjects with liver metastases
Albumin	$\geq 2.5 \text{ mg/dL}$
Coagulation	
International Normalized Ratio (INR) or Prothrombin Time (PT)	$\leq 1.5 \times \text{ULN}$ unless subject is receiving anticoagulant therapy as long as PT or PTT is within therapeutic range of intended use of anticoagulants
Activated Partial Thromboplastin Time (aPTT)	$\leq 1.5 \times \text{ULN}$ unless subject is receiving anticoagulant therapy as long as PT or PTT is within therapeutic range of intended use of anticoagulants
aCreatinine clearance should be calculated per institutional standard.	

- Female subject of childbearing potential should have a negative urine or serum pregnancy within 72 hours prior to receiving the first dose of study medication. If the urine test is positive or cannot be confirmed as negative, a serum pregnancy test will be required.
- Female subjects of childbearing potential should be willing to use 2 methods of birth control or be surgically sterile, or abstain from heterosexual activity for the course of the study through 120 days after the last dose of study medication (Reference Section in Appendix 3). Subjects of childbearing potential are those who have not been surgically sterilized or have not been free from menses for > 1 year.
- Male subjects should agree to use an adequate method of contraception starting with the first dose of study therapy through 120 days after the last dose of study therapy.

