5.3 Subject Exclusion Criteria

The subject must be excluded from participating in the trial if the subject:

- A history of anaphylaxis to olaparib
- Is currently participating and receiving study therapy or has participated in a study of an investigational agent and received study therapy or used an investigational device within 4 weeks of the first dose of treatment.

A Phase II, Single-arm Study of Combination Pembrolizumab and Olaparib in the Treatment of Patients with Advanced Cholangiocarcinoma

Version 2.1: 17Mar2023

3. A woman of childbearing potential (WOCBP) who has a positive urine pregnancy test within 72 hours prior to 1st dose of treatment (see Appendix 3). If the urine test is positive or cannot be confirmed as negative, a serum pregnancy test will be required.
4. Has a known history of active TB (Bacillus Tuberculosis).
5. Has known hypersensitivity to pembrolizumab or any of its excipients.
6. Has had a prior anti-cancer monoclonal antibody (mAb) within 4 weeks prior to study Day 1 or who has not recovered (i.e., \leq Grade 1 or at baseline) from adverse events due to agents administered more than 4 weeks earlier.
7. Has had prior chemotherapy, targeted small molecule therapy, or radiation therapy within 2 weeks prior to study Day 1 or who has not recovered (i.e., \leq Grade 1 or at baseline) from adverse events due to a previously administered agent.

NOTE: Subjects with \leq Grade 2 neuropathy are an exception to this criterion and may qualify for the study.

NOTE: If subject received major surgery, they must have recovered adequately from the toxicity and/or complications from the intervention prior to starting therapy.

8. Has a known additional malignancy that is progressing or requires active treatment. Exceptions include basal cell carcinoma of the skin or squamous cell carcinoma of the skin that has undergone potentially curative therapy or in situ cervical cancer.

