7.1.3 Laboratory Procedures/Assessments

Details regarding specific laboratory procedures/assessments to be performed in this trial are provided below.

Laboratory tests for hematology, chemistry, urinalysis, and others are specified in Table 6.

A Phase II, Single-arm Study of Combination Pembrolizumab and Olaparib in the Treatment of Patients with Advanced Cholangiocarcinoma
 Version 2.1: 17Mar2023

Table 6 Laboratory Tests

Hematology	Chemistry	Urinalysis	Other
Hematocrit	Albumin	Blood	Serum β -human chorionic gonadotropin†
Hemoglobin	Alkaline phosphatase	Glucose	(β -hCG)†
Platelet count	Alanine aminotransferase (ALT)	Protein	PT (INR)
WBC (total and differential)	Aspartate aminotransferase (AST)	Specific gravity	aPTT
Red Blood Cell Count		Microscopic exam (If abnormal)	Total triiodothyronine (T3)
Absolute Neutrophil Count	Carbon Dioxide ‡	results are noted	Free thyroxine (T4)
Absolute Lymphocyte Count	(CO_2 or bicarbonate)	Urine pregnancy test †	Thyroid stimulating hormone (TSH)
			PK
	Calcium		
	Chloride		Blood for correlative studies
	Glucose		
	Phosphorus		
	Potassium		
	Sodium		
	Total Bilirubin		
	Direct Bilirubin (If total bilirubin is elevated above the upper limit of normal)		
	Total protein		
	Blood Urea Nitrogen		

† Perform on women of childbearing potential only. If urine pregnancy results cannot be confirmed as negative, a serum pregnancy test will be required.

‡ If considered standard of care in your region.

A Phase II, Single-arm Study of Combination Pembrolizumab and Olaparib in the Treatment of

Patients with Advanced Cholangiocarcinoma

Version 2.1: 17Mar2023

Laboratory tests for screening or entry into the Second Course Phase should be performed within 10 days prior to the first dose of treatment. After Cycle 1, pre-dose laboratory procedures can be conducted up to 72 hours prior to dosing. Results must be reviewed by the investigator or qualified designee and found to be acceptable prior to each dose of trial treatment.

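### Flow-chart footnote 4 makes the screening pregnancy test conditional, contradicting Section 5.2 and Appendix 3, and the chart schedules none of Appendix 3's later tests

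*Combined protocol and SAP*

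**What the plan says.** **Baseline test.** Footnote 4 of the flow chart (Section 6.1) applies to women of childbearing potential and asks for a urine or serum test "WITHIN 28 DAYS OF REGISTRATION AND ONLY IF CLINICALLY APPROPRIATE". Section 5.2 opens with "Subject must meet all of the following applicable inclusion criteria to participate in this study", and one of its criteria is that such women "should have a negative urine or serum pregnancy within 72 hours prior to receiving the first dose of study medication". Section 5.3, exclusion 3, uses the same interval: it excludes a woman "who has a positive urine pregnancy test within 72 hours prior to 1st dose of treatment". Appendix 3 (Pregnancy Testing) allows these women in only once a highly sensitive test is negative and, where applicable, wants it repeated no more than 24 hours before first dose. The laboratory table that follows the chart footnotes says of the pregnancy tests "Perform on women of childbearing potential only", with no further condition.

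**General laboratory windows.** Criterion 8 of Section 5.2 states "All screening labs will be performed within 28 days of registration". Section 7.1.3 states "Laboratory tests for screening or entry into the Second Course Phase should be performed within 10 days prior to the first dose of treatment"; this can be read as covering all screening tests or the Second Course alone.

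**Later tests.** The flow-chart row for the pregnancy test is marked under Screening and nowhere else. Appendix 3 says further tests will be done each month during treatment and again after the last dose, with the number of days left as [X days]. It also calls for a test after a missed cycle or on suspicion of pregnancy.

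**The concern.** Footnote 4 is already limited to women of childbearing potential, so its extra condition cannot mean that they are the ones to be tested. It can only exempt some of them, and Section 5.2 and Appendix 3 provide no such exemption.

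The chart matters because Section 5.4.1 has each Day 1 dose follow completion of the procedures detailed there, and Section 7.1.5 sends sites to it for visit requirements. A site working from the chart could take the baseline test as optional and would do no routine tests afterwards.

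The stake is fetal exposure. Sections 9.1.1.1.6 and 9.1.1.2.5 say that pembrolizumab and olaparib can each cause fetal harm. Section 4.3.1.2 reports reduced embryofetal survival and major malformations in rats given olaparib, at exposures below the clinical level. Sections 5.3.2 and 5.6 require study treatment to stop on pregnancy, and that stop depends on detection. Section 7.2.2 asks for reports of pregnancies that come to the site spontaneously. Without scheduled tests, detection rests on a missed period, symptoms or self-report.

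**Working it through.** This is a comparison of texts; the plan states no figure to reproduce.

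**Step 1: is the baseline wording in conflict?** Two elements of footnote 4 need separate treatment.

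- *The window.* The footnote counts 28 days from registration; Section 5.2 counts 72 hours back from first dose. A site can do a screening test in the first window and another in the second, and one test close to dosing can satisfy both. The 28 days is also the general screening-laboratory window in criterion 8. No conflict.
- *The condition.* The footnote lets the test be omitted when it is not judged clinically appropriate. Section 5.2 requires a negative result, and Appendix 3 makes one a precondition of inclusion. A woman with no test has no negative result. Direct conflict.

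The criterion itself says that the woman should have a negative test, but the heading of its list is mandatory and there is no discretion clause. Exclusion 3 is a weaker safeguard, because only a positive result triggers it.

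**Step 2: what does the chart schedule after baseline?**

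| Period | Flow chart | Appendix 3 |
|---|---|---|
| Screening | 1 mark, conditional under footnote 4 | negative test required; 24-hour repeat where applicable |
| On treatment | 0 | monthly |
| Follow-up | 0 | 1, day not filled in |

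**Step 3: illustrative counts per woman.** These count tests after first dose and before treatment ends, with a month of 30.44 days and cycles of 21 days. Treatment length has to be assumed. One value is 24 weeks, borrowed from the PFS hypothesis in Section 3.2. The other is 12 months, from the average treatment length of 12 in the Trial Summary, which has no unit.

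- 24 weeks = 168 days. Monthly: 168 / 30.44 = 5.5, so 5 tests. Each Day 1 from cycle 2: 168 / 21 = 8 cycles, so 7 tests.
- 12 months = 12 × 30.44 = 365 days. Monthly: 11 tests, as the twelfth falls at the end. Each Day 1 from cycle 2: 365 / 21 = 17.4, so 17 tests.

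The chart gives 0 in both cases. Neither length is a maximum: Section 5.6 allows 35 pembrolizumab treatments, and Section 5.4.3.1 allows up to 17 further cycles.

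**Step 4: is there a visit for the post-treatment test?** Follow Up Visit 1 is 30 days after the last dose. Visit 2 is 6 weeks later, at about 30 + 42 = 72 days. Urinalysis is already marked at both visits and at each Day 1. The contraception criteria in Section 5.2 run to 120 days after the last dose, and no chart column after Visit 2 carries a laboratory mark.

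**The case against.** The strongest reply is that the baseline risk is largely closed elsewhere. Section 5.2 must be met in full, exclusion 15 bars any pregnant woman, Appendix 3 requires a negative test before inclusion, Section 7.1.1.2 requires review of every criterion, and Section 7.1 says that the chart only summarises procedures. This stands. A reader might infer from footnote 4 that the protocol lets an untested woman be enrolled, or that it accepts a test some four weeks old in place of the 72-hour one. The documents support neither: both come from reading the footnote alone, and under the whole protocol a woman without a recent negative test is ineligible.

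The second reply is that Appendix 3 is visibly unfinished. It has [X days], references to a Section X, and two competing contraception paragraphs for women, so the monthly rule may be leftover template text. That also stands in part: the documents do not show which text is wrong. But Sections 5.2, 5.3 and 5.3.1.2 send sites to this appendix, and its monthly rule is written as something that will happen. One of the two texts has to change. The baseline safeguards do not help here, because eligibility review is over before the later tests fall due.

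Third, contraception requirements, testing on suspicion and mandatory discontinuation give some protection on treatment. They do, but they are not a routine testing schedule.

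**Conclusion.** The point holds in two parts. First, footnote 4's discretionary condition contradicts Section 5.2 and Appendix 3. It is an error in the schedule that sites use, not the absence of a baseline requirement, and the 28-day window is not part of the conflict. Second, the chart omits every on-treatment and post-treatment test in Appendix 3, and the post-treatment test has no date anywhere. This is the larger practical gap, because nothing else in the plan would reveal a missed routine test.

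The size is 0 scheduled on-treatment tests per woman against 5 (24 weeks) or 11 (12 months) under the monthly rule, and 0 against 1 after treatment. These counts rest on the assumed treatment lengths and on Appendix 3 being intended. The documents do not say how many of the 36 participants will be women of childbearing potential.

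Sample size, response assessment and primary analysis are unaffected. This is a patient-safety correction that should be made; it does not bear on the validity of the results.

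**What to change.** 1. **Footnote 4.** Delete the clinical-appropriateness condition and require, for all women of childbearing potential, a negative urine or serum test in the 72 hours before first dose. In Section 7.1.3, state that the pregnancy test alone follows this window; tightening the 10-day sentence as a whole would move the window for every test in Table 6. Reconcile the 24-hour repeat in Appendix 3 with the same rule.
2. **Later tests.** Mark the pregnancy test in the On Treatment column at least monthly. Each cycle's Day 1 is convenient, since Section 7.1.3 already allows pre-dose laboratory work up to 72 hours ahead after Cycle 1. Add one post-treatment test at Follow Up Visit 1 (about 30 days) or Visit 2 (about 72 days), and fill in [X days] to match. If the sponsor did not intend these tests, amend Appendix 3 instead.
3. **Same appendix.** Replace the Section X references and keep one contraception paragraph for women that agrees with Section 5.2.

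The cost is a footnote edit, one chart row, one sentence in Section 7.1.3 and a tidied appendix. Testing at every Day 1 instead of monthly adds 7 − 5 = 2 urine tests per woman over 24 weeks, or 17 − 11 = 6 over 12 months. No new visit is needed if the post-treatment test is placed at Visit 1 or 2. A date near the 120-day end of contraception would need an extra contact or a remote test.
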